7.3.3 Medical History

A by-subject listing of general medical history for all randomized subjects will be provided.

7.3.4 Prior Therapy Agents

Prior adjuvant or neo-adjuvant therapy will be summarized by treatment group and overall.

Prior systemic cancer therapy will be summarized by treatment group and overall and listed by subject.

Prior radiotherapy and prior surgery related to cancer will be listed by subject.

7.3.5 Physical Examinations

Subjects with abnormal baseline physical examination will be listed by subject.

7.3.6 Baseline Physical Measurements

Baseline physical measurements will be listed by subject.

7.4 Extent of Exposure

Listings will include all available exposure data. Analyses will be performed by treatment group “as treated” in all treated subjects, unless otherwise specified.

7.4.1 Administration of Study Therapy

The following parameters will be summarized (descriptive statistics) by study therapy and treatment group:

- Number of doses received
- Cumulative dose
- Relative dose intensity (%) using the following categories: < 50%; 50 - < 70%; 70 - < 90%; 90 - < 110%; ≥ 110%
- Average daily dose

Duration of study therapy will be summarized (descriptive statistics) by treatment group.

A by-subject listing of dosing of study medication (record of study medication, infusion details, and dose changes) will be also provided.

Note that similar study therapy table will be summarized for all intermediate/poor risk treated subjects in Arm A and Arm C.

Table 7.4.1-1: Study Therapy Parameter Definitions for Arm A and C

	Nivolumab	Cabozantinib	Sunitinib
Dosing Schedule per Protocol	240 mg every 2 weeks	40 mg PO once daily	50 mg PO once daily for 4 weeks followed by 2 weeks off.
Dose	mg	mg	mg
Cumulative Dose	mg sum of the doses administered to a subject	mg sum of the doses administered to a subject	mg sum of the doses administered to a subject
Relative Dose Intensity (%)	$[\text{Cum dose (mg)} / ((\text{Last dose date} - \text{First dose date} + 14) \times 240/14)] \times 100$	See below	See below
Duration of Treatment	Last dose date - Start dose date + 1	Last dose date - Start dose date + 1	Last dose date - Start dose date + 15

Additional Parameters -Cabozantinib treatment

Average daily dose (in mg/day) is defined as:

Sum of all Cabozantinib doses in mg actually received / duration of treatment in days.

Since Cabozantinib treatment consists of 40 mg PO daily dose, the planned dose intensity of Cabozantinib is 40 mg/day.

Relative dose intensity for Cabozantinib (%) is defined as: $(Average\ daily\ dose / 40) \times 100$.

Additional Parameters -Sunitinib treatment

Average daily dose (in mg/day) is defined as:

Sum of all Sunitinib doses in mg actually received / duration of treatment in days

Since Sunitinib treatment consists of 50 mg PO daily dose for 4 weeks followed by 2 weeks of washout period, the planned dose intensity of Sunitinib is 33.33 mg/day (50 mg x 28 days / 42 days).

Relative dose intensity for Sunitinib (%) is defined as: $(Average\ daily\ dose / 33.33) \times 100$.

Table 7.4.1-2: Study Therapy Parameter Definitions for Arm B (Cycle 1-4)

	Nivolumab	Ipilimumab	Cabozantinib
Dosing Schedule per Protocol	3 mg/kg every 3 weeks for 4 doses	1 mg/kg every 3 weeks for 4 doses	40 mg PO once daily
Dose	Dose (mg/kg) is defined as Total Dose administered (mg)/Most recent weight (kg). Dose administered in mg at each dosing date and weight are collected on the CRF.	Dose (mg/kg) is defined as Total Dose administered (mg)/Most recent weight (kg). Dose administered in mg at each dosing date and weight are collected on the CRF.	mg
Cumulative Dose	Cum Dose (mg/kg) is the sum of the doses administered to a subject.	Cum Dose (mg/kg) is the sum of the doses administered to a subject.	mg sum of the doses administered to a subject
Cycle Duration _(i) (wk)	$(Dose\ date_{(i+1)} - Dose\ date_{(i)})/7$	$(Dose\ date_{(i+1)} - Dose\ date_{(i)})/7$	N/A
Cycle Intensity _(i) (mg/kg/wk)	Dose _(i) /Cycle Duration _(i)	Dose _(i) /Cycle Duration _(i)	N/A
Relative Cycle Intensity _(i) (%)	$(Cycle\ Intensity_{(i)}/intended\ dose\ per\ week_{(i)}) * 100$	$(Cycle\ Intensity_{(i)}/intended\ dose\ per\ week_{(i)}) * 100$	N/A
Relative Dose Intensity (%)	Sum of all Relative Cycle Intensities divided by N	Sum of all Relative Cycle Intensities divided by N	$(Average\ daily\ dose / 40) \times 100$
Duration of Treatment	Last dose date - Start dose date +1	Last dose date - Start dose date +1	Last dose date - Start dose date +1

Table 7.4.1-3: Study Therapy Parameter Definitions for Arm B (Cycle 5 Onward)

	Nivolumab	Cabozantinib
Dosing Schedule per Protocol	240 mg every 2 weeks	40 mg PO once daily
Dose	mg	mg
Cumulative Dose	mg sum of the doses administered to a subject	mg sum of the doses administered to a subject
Relative Dose Intensity (%)	$[\text{Cum dose (mg)} / ((\text{Last dose date} - \text{First dose date} + 14) \times 240/14)] \times 100$	$(\text{Average daily dose} / 40) \times 100$
Duration of Treatment	Last dose date - Start dose date + 1	Last dose date - Start dose date + 1

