10 STATISTICAL CONSIDERATIONS

10.1 Sample Size Determination

The sample size of this study accounts for the primary endpoint of progression-free survival (PFS) per BICR in all randomized participants. Assuming a 25% screen failure rate, it is expected that approximately 850 participants will need to be enrolled in order to randomize 638 participants (319 per arm) in a 1:1 ratio. To represent the normal frequency of the favorable risk group in mRCC, the favorable risk participants are capped at approximate 25%; thus, at most 212 favorable risk participants (106 per arm) will be enrolled to randomize 160 favorable risk participants in a 1:1 ratio. The rest of the enrolled participants will provide approximately 478 intermediate/poor risk randomized participants (239 per each arm).

The overall alpha for this study is 0.05 (two-sided). PFS will be evaluated for treatment effect at an alpha of 0.05 (two-sided), with at least 95% power. No interim analysis of PFS is planned. OS will be evaluated for treatment effect at an alpha level of 0.05 (two-sided) with 80% power, accounting for two formal interim analyses to assess efficacy.

Sample Size Justification for Primary PFS Endpoint

The primary endpoint of PFS per BICR of Arm A versus Arm C analysis will be conducted on all randomized participants. The PFS analysis will occur after approximately 9-10 months minimum follow-up on all randomized subjects by which approximately 350 events from Arm A and Arm C are expected. The 350 PFS events provide at least 95% power to detect a HR of 0.68 for PFS of Arm A versus Arm C with a type I error of 0.05 (two-sided). The HR of 0.68 corresponds to a 47% increase in the median PFS, assuming a median PFS of 18.2 months for Arm A and 12.4 months for Arm C. It is projected that an observed HR of 0.811 or less, which corresponds to a 2.89 month or greater improvement in median PFS (12.4 versus 15.3 months), would result in a statistically significant improvement in PFS for the Arm A versus Arm C comparison.

If the formal analysis of PFS among all randomized participants is statistically significant, the formal interim analysis of OS among all randomized participants will be tested, as per hierarchical testing procedure.

Sample Size Computation for Secondary OS Endpoint

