7.4.2 Modifications of Study Therapy

7.4.2.1 Dose Delays

Each nivolumab infusion or sunitinib dose may be delayed. A dose will be considered as actually delayed if the delay is exceeding 3 days (ie greater than or equal to 4 days from scheduled dosing date) for nivolumab. Reason for dose delay will be retrieved from CRF dosing pages. It is worth noting that during the two week mandatory washout period for sunitinib, a daily dose of 0 mg will be entered in the CRF pages, with corresponding reason for dose modification recorded as “No Change”.

If cabozantinib is given daily, a daily dose of 0 mg entered in the CRF pages will be considered as delay. If cabozantinib is given every other day, then a daily dose of 0 mg will be entered every other day in the CRF pages, with corresponding reason for dose modification recorded as “No Change”. If there are more than one 0 mg daily dose entered consecutively, then this will be considered as delay.

The following parameters will be summarized by treatment group:

- Number of subjects with at least one dose delayed, the number of dose delays per subject, the reason for dose delay and the length of dose delay.

Note that similar dose delay summary table for Arm A and Arm C will be summarized for all intermediate/poor risk treated subjects.

For Arm B, both nivolumab and ipilimumab can be delayed at the same cycle. A dose will be considered as actually delayed if the delay is exceeding 3 days (ie greater than or equal to 4 days from scheduled dosing date) for nivolumab and ipilimumab. Cabozantinib a daily dose of 0 mg entered in the CRF pages will be considered as delay. Similar table will be produced for Arm B

subjects previously randomized to Arm B continue with Arm B treatment and continue with Arm B clinical planned events, per protocol.

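### The sunitinib duration rule always adds 14 rest days, so average daily dose and relative dose intensity are understated when treatment stops part-way through an on-period

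*SAP*

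**What the plan says.** SAP Section 7.4.1 gives the sunitinib schedule as "50 mg PO once daily for 4 weeks followed by 2 weeks off". Table 7.4.1-1 sets sunitinib duration of treatment at "Last dose date - Start dose date + 15", with no condition on the cycle day of the last dose. For nivolumab and cabozantinib the duration is last dose date minus start dose date plus 1.

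Average daily sunitinib dose is "Sum of all Sunitinib doses in mg actually received / duration of treatment in days". RDI is that average divided by 33.33 mg/day, times 100. RDI is also reported in categories with cut points at 50, 70, 90 and 110%. Number of doses, cumulative dose and duration of study therapy are summarised as well, and similar tables are produced for intermediate/poor-risk treated participants.

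Two other places bear on the point. For nivolumab, the same table keeps the RDI denominator (+14) apart from the duration (+1). SAP Section 7.4.2.1 says that "during the two week mandatory washout period for sunitinib, a daily dose of 0 mg will be entered in the CRF pages". The text does not say whether the last dose date means the last non-zero dose.

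**The concern.** The constant 15 is the usual inclusive +1 plus a fixed 14 days for the rest period. Those 14 days are earned by 28 days of dosing. If the last dose comes on day 7 of an on-period, the rule still charges the whole rest period against 7 days of drug and compares the result with a planned average that assumes 28 on and 14 off. A participant who took every planned dose up to stopping is then reported as under-dosed.

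The trial is open-label, and a reader of the study report may look at the dose intensity delivered in the control arm. Under-dosing that did not occur would appear there for sunitinib only. For cabozantinib, which has no rest period, the +1 rule gives a compliant participant 100% on any stop day.

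**Working it through.** **Inputs** (SAP Section 7.4.1): 50 mg daily, 28 days on and 14 off; duration = last − start + 15; planned intensity 33.33 mg/day.

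**Planned figure.** 50 × 28 / 42 = 33.33 mg/day, as the SAP states.

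**Formula.** Take a participant with no missed or delayed doses whose last dose is on on-drug day d (1 to 28) of cycle k.

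- Doses taken: n = 28(k − 1) + d
- SAP duration: D = 42(k − 1) + d + 14
- RDI = (50 × n / D) / 33.33 × 100

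Since 50 / 33.33 = 1.5, the shortfall from 100% is (D − 1.5n) / D = (14 − d/2) / D. It is zero at d = 28, positive at every earlier day, and shrinks as cycles accumulate.

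| Last dose | n | D | Average mg/day | RDI |
|---|---|---|---|---|
| Cycle 1 day 7 | 7 | 21 | 16.67 | 50.0% |
| Cycle 1 day 14 | 14 | 28 | 25.00 | 75.0% |
| Cycle 1 day 21 | 21 | 35 | 30.00 | 90.0% |
| Cycle 2 day 7 | 35 | 63 | 27.78 | 83.3% |
| Cycle 2 day 14 | 42 | 70 | 30.00 | 90.0% |
| Cycle 3 day 6 | 62 | 104 | 29.81 | 89.4% |
| Cycle 3 day 14 | 70 | 112 | 31.25 | 93.8% |
| Cycle 4 day 1 | 85 | 141 | 30.14 | 90.4% |
| Cycle 9 day 1 | 225 | 351 | 32.05 | 96.2% |
| Day 28 of any cycle | 28k | 42k | 33.33 | 100% |

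**Category shifts.** RDI is falsely below 90% for stops up to day 20 of cycle 1, day 13 of cycle 2 and day 6 of cycle 3: 20 + 13 + 6 = 39 of the 84 on-drug days in the first three cycles. From cycle 4 there are none. From cycle 8 every stop day gives at least 95%.

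**Arm level.** This needs a distribution of time on drug, which the documents do not give. I assumed exponential stopping and full compliance, with medians from 3 months up to 12.4 months. The upper value borrows the control-arm design assumption in Protocol Section 10.1 ("assuming a median PFS of 18.2 months for Arm A and 12.4 months for Arm C") as a proxy for time on drug.

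| Assumed median (months) | Mean RDI | Falsely below 90% |
|---|---|---|
| 3 | 90.8% | 23% |
| 6 | 94.4% | 13% |
| 9 | 95.9% | 9% |
| 12.4 | 96.8% | 7% |

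**Would +1 alone repair RDI?** No. With +1, a compliant participant gets 150% throughout the cycle 1 on-period, 112.5% at cycle 2 day 14 and 105.0% at cycle 4 day 14.

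**Would pro-rating?** Replacing 14 by d/2 gives a denominator of 42(k − 1) + 1.5d = 1.5n, so RDI is 100% at every d and k.

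**Last dose date.** If a 0 mg washout record counted as the last dose, the rest period would be charged twice. Even completed cycles would then fall short: 1400 / 56 / 33.33 = 75.0% after one cycle and 5600 / 182 / 33.33 = 92.3% after four.

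**The case against.** The case for leaving the rule alone has real substance.

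- **Closing the last dosing interval is legitimate.** Nivolumab RDI also extends its denominator, by 14 days. The difference from cabozantinib's +1 follows from the regimens and is not an error in itself. This stands. The defect is only that the 14 days are unconditional.
- **The effect fades.** If 12.4 months approximates time on drug, that is 12.4 × 30.4375 / 42, or about nine cycles, where the worst value is 96.2%. This stands; the large errors belong to early stops.
- **Stops may cluster at cycle ends.** Scans at Week 12 and then every 6 weeks to Week 60 (Protocol Table 2-4) fall near cycle boundaries. Stopping for progression before the next cycle starts leaves the last dose on day 28 and RDI at 100%. The exponential calculation ignores this. Scan windows, reading time, cycle delays and stops for toxicity weaken the alignment, so it is only a partial mitigation.
- **Duration is also reported without the padding.** SAP Section 7.5.6 plans a Kaplan-Meier analysis of time to discontinuation with last dose date as the event. This is true, but it leaves sunitinib duration defined in two ways 14 days apart, and it does nothing for RDI.
- **These are descriptive summaries with by-subject dosing listings behind them.** This is true and limits the importance. It does not make the tabulated figure right.

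A reader might infer that the rule biases control-arm exposure downward as a whole. The documents do not support that. Only average daily dose and RDI fall; number of doses and cumulative dose do not use duration, and the duration summary moves the other way, up by 14 days.

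**Conclusion.** The point holds as a minor error in a stated formula. For a fully compliant participant who stops during an on-period, average daily dose and RDI are understated, never overstated. The RDI shortfall is 50 points at cycle 1 day 7 and 16.7 points at cycle 2 day 7, at most 10 points from cycle 4, and nil after a completed on-period. No other section of the SAP corrects RDI.

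The participant-level figures rest only on the SAP's definitions, full compliance and no cycle delays, with the last dose read as the last non-zero dose. The arm-level range of about 3 to 9 points of mean RDI rests on assumed stopping times and should be read as an indication of scale.

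It would be wrong to infer that the efficacy comparison is affected: no PFS, OS or ORR test uses dose intensity.

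**What to change.** In SAP Table 7.4.1-1 and the sunitinib parameter text:

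1. Define sunitinib RDI as cumulative dose received divided by planned cumulative dose from first to last non-zero dose date on the 4-weeks-on/2-weeks-off schedule, times 100.
2. If an average daily dose is still to be compared with 33.33 mg/day, pro-rate the final rest days: add half the number of days from the start of the last on-period to the last non-zero dose, in place of a fixed 14.
3. Report duration of treatment as last non-zero dose date minus start date plus 1, as for the other drugs and separate from the RDI denominator, as the table already does for nivolumab.

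The SAP should also state how a delayed cycle start counts, because items 1 and 2 can then differ. Suppose cycle 2 starts 14 days late and is completed on day 84. On a fixed calendar, planned and received doses through day 84 are both 56, so item 1 gives 100%. Item 2 gives 56 × 50 / 98 / 33.33 = 85.7%.

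Adding the 14 days only after a completed 28-day block is not a remedy. In cycle 1, duration would jump from 27 to 42 days between a stop on day 27 and one on day 28, and the average daily dose for every earlier compliant stop would be 50 mg against a planned 33.33.

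The cost is a formula change and minor programming, with no new data.

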7.4.2 Modifications of Study Therapy

7.4.2.1 Dose Delays

Each nivolumab infusion or sunitinib dose may be delayed. A dose will be considered as actually delayed if the delay is exceeding 3 days (ie greater than or equal to 4 days from scheduled dosing date) for nivolumab. Reason for dose delay will be retrieved from CRF dosing pages. It is worth noting that during the two week mandatory washout period for sunitinib, a daily dose of 0 mg will be entered in the CRF pages, with corresponding reason for dose modification recorded as “No Change”.

If cabozantinib is given daily, a daily dose of 0 mg entered in the CRF pages will be considered as delay. If cabozantinib is given every other day, then a daily dose of 0 mg will be entered every other day in the CRF pages, with corresponding reason for dose modification recorded as “No Change”. If there are more than one 0 mg daily dose entered consecutively, then this will be considered as delay.

The following parameters will be summarized by treatment group:

- Number of subjects with at least one dose delayed, the number of dose delays per subject, the reason for dose delay and the length of dose delay.

Note that similar dose delay summary table for Arm A and Arm C will be summarized for all intermediate/poor risk treated subjects.

For Arm B, both nivolumab and ipilimumab can be delayed at the same cycle. A dose will be considered as actually delayed if the delay is exceeding 3 days (ie greater than or equal to 4 days from scheduled dosing date) for nivolumab and ipilimumab. Cabozantinib a daily dose of 0 mg entered in the CRF pages will be considered as delay. Similar table will be produced for Arm B

subjects previously randomized to Arm B continue with Arm B treatment and continue with Arm B clinical planned events, per protocol.

7.4.2.2 Infusion Interruptions and Rate Changes

Each nivolumab or ipilimumab infusion can be interrupted and/or the IV infusion rate can be reduced. This information will be retrieved from CRF dosing pages.

The following parameters will be summarized by treatment group:

- Number of subjects with at least one dose infusion interruption, the reason for interruption, and the number of infusion interruptions per subject.
- Number of subjects with at least one IV infusion rate reduction, the reason for reduction and the number of infusion with IV rate reduction per subject.

Note that similar summary table for Arm A and Arm C will be summarized for all intermediate/poor risk treated subjects.

7.4.2.3 Dose Escalations

Dose escalations are permitted for cabozantinib and sunitinib but not for nivolumab and ipilimumab.

7.4.2.4 Dose Reductions

Dose reductions are permitted for cabozantinib and sunitinib but not for nivolumab and ipilimumab.

Dose reduction for subjects treated with sunitinib is defined as at least one day with a non zero dose smaller than 50 mg and smaller than previous non zero dose with a CRF reason different from “Dosing Error” or “No Change”.

Dose reduction for subjects treated with cabozantinib is defined as at least one day with 20 mg or 20 mg every other day with a CRF reason different from “Dosing Error” or “No Change”.

Note that similar dose reduction summary table for Arm A and Arm C will be summarized for all intermediate/poor risk treated subjects.

The following summaries will be presented for the cabozantinib component of study treatment:

- i) For dose reductions due to AE

Categorical summaries for:

- Subjects with any dose reduction
- Dose levels received by a subject
- Lowest non-zero dose level received
- Last non-zero dose level received
- Last dose level received (including dose holds)

Descriptive statistics for:

- Duration of treatment in months for each dose level (40 mg, 20 mg, 0 mg)
- Time to second dose level reduction (first receipt of 20mg) (days)
- ii) Summaries for dose holds due to AE (those with 0 mg due to AE):
 - Descriptive statistics for number of dose holds due to an AE
 - Descriptive statistics for duration of dose holds per dose hold and per subject due to an AE, calculated as (stop date of hold – start date of hold + 1)
 - Categorical summary for subjects with duration of holds due to an AE that can be classified as any number of days, ≥ 7 days, ≥ 14 days, ≥ 21 days, and >42 days
 - Descriptive statistics for time to first dose hold, time to first dose hold that ≥ 7 days, ≥ 14 days, ≥ 21 days, and >42 days. The time to dose hold is calculated as (start date of the hold – first dose date + 1)
 - Descriptive statistics for time to second dose hold, time to second dose hold that was ≥ 7 days, ≥ 14 days, ≥ 21 days, and >42 days.
- iii) Summaries for dose modifications (defined as a reduction or hold) due to AE:
 - Frequency counts and percentages for subjects with any dose modifications
 - Descriptive statistics for number of dose modifications (0-3)
 - Descriptive statistics for time to the first dose modification
 - Descriptive statistics for time to the second dose modification

7.4.2.5 Dose Omissions

Dose omissions are not permitted.

[REDACTED]

[REDACTED]

[REDACTED]

[REDACTED]

[REDACTED]

[REDACTED]

[REDACTED]

[REDACTED]

[REDACTED]

[REDACTED]

[REDACTED]

[REDACTED]

[REDACTED]

7.5 Efficacy

Analyses in this section will be tabulated for all randomized subjects in Arm A and Arm C, unless otherwise specified. A few separate efficacy summary tables will be generated for those subjects who randomized to Arm B prior to Revised Protocol 01, which is specified in the relevant subsections below.

Principal analyses of progression free survival (PFS) and objective response rate (ORR) will be based on the Blinded Independent Central Review (BICR) evaluation, unless noted otherwise.

Analyses in this section will be tabulated for all randomized subjects by treatment group as randomized, unless otherwise specified.

Unless stated otherwise, whenever a stratified analysis is specified, the following stratifications factors (recorded at randomization as per IRT) will be used:

- IMDC Prognostic Score: 0 versus 1-2 versus 3-6
- Region: US/Canada/W Europe/N Europe versus ROW
- PD-L1 tumor expression: $\geq 1\%$ versus $< 1\%$ or indeterminate

The key secondary objective Overall Survival among all randomized subjects will be tested after conducting the primary objective analyses of PFS on all randomized subjects. For assessing this secondary objective of this study, a hierarchical testing procedure¹⁰ will be used so that the overall experiment-wise Type I error rate is two-sided 0.05.

The secondary objective of ORR among all randomized subjects will be tested after conducting the key secondary objective analyses of OS on all randomized subjects, per a hierarchical testing procedure so that the overall experiment-wise Type I error rate is two-sided 0.05. Note that the formal ORR analysis specified in the SAP supersede those specified in the protocol.

Confidence intervals (CI) for primary and secondary endpoint analyses included in hierarchy will be based on nominal significance level adjusted for primary endpoints and interim analyses to preserve overall type one error rate.

Alpha (α) for the CI will be the same as nominal significance level for hypothesis testing. CIs for other endpoints will be at the two-sided 95% level. All p-values reported will be two-sided. P-values will be rounded to the fourth decimal place. Point estimates and confidence bounds for efficacy variables will be rounded to the second decimal place.

A by-subject listing of efficacy results will be presented including treatment group, treatment duration, BICR progression date, overall survival, death date, etc.

